4.1 Rationale for study design

Table 4-1 Rationale for study design

Study Design Aspect	Rationale
Overall	This is a randomized, placebo-controlled, participant-and investigator-blinded, sponsor open-label study to evaluate the safety, tolerability, and efficacy of different MBL949 dosing regimens in obese participants with or without T2DM. In this study, a subcutaneous injection of MBL949 or placebo is planned at biweekly dosing intervals for 14 weeks to study the effect of MBL949 on weight loss. The design (5 different MBL949 treatment arms and placebo) allows assessment of the safety, tolerability and efficacy of different up titration regimens modelled to reach three different steady state plasma concentrations. This will help determine the optimal dosing regimen for MBL949. The randomized and blinded study design was chosen to minimize bias.
Randomization	Commercially Confidential Information The randomization strategy as defined in Section 3 will maximize the statistical power for detecting differences in each strata while avoiding allocation bias.
Blinding	Blinding of participants and the investigator allows for an unbiased assessment of study endpoints, particularly for participant readouts such as adverse events and patient-reported outcomes. The blinding table, as detailed in Table 6-3 and will improve the accuracy of safety-related decisions during trial conduct, if needed.
Duration of study periods	Participants will be treated over a period of 14 weeks. The treatment period of 14 weeks followed by a 10 week evaluation period will allow adequate safety and efficacy data to be collected to assess the future potential of MBL949 in obesity-related disorders. This trial duration is comparable to the early assessment of weight loss efficacy identified in studies of weight loss agents. CCI

Study Design Aspect	Rationale
Placebo comparator	The use of placebo as a comparator is to provide a comparison group for the collection and assessment of safety, tolerability, and efficacy data while avoiding historical comparisons and helps to distinguish time-effects from drug effects.

4.2 Rationale for dose/regimen and duration of treatment

Commercially Confidential Information

All 5 proposed dosing arms consist of a total of 8 bi-weekly SC injections over 14 weeks, followed by a 10 week follow-up period with primary endpoint evaluation at week 16.

Commercially Confidential Information

Commercially Confidential Information

4.3 Rationale for choice of control drugs (comparator/placebo) or combination drugs

The use of a placebo comparator allows for a comparison group of safety effects. An excipient matched placebo will be used to evaluate the benefit of MBL949 beyond any potential physiologic effect of the excipients,

CCI

Commercially Confidential Information

4.4 Purpose and timing of interim analyses/design adaptations

Commercially Confidential Information

4.5 Risks and benefits

There may be a benefit of weight loss and improvement in metabolic parameters for participants in this study.

Commercially Confidential Information

It is hoped that this study will benefit individuals with obesity through weight loss and thereby lead to a new therapeutic approach to treat obesity related comorbidities.

Risks to participants are minimized by the appropriate eligibility criteria and specific dose-limiting toxicity definitions, as well as specific guidelines for dosing holidays as well as stopping rules, and are included in this protocol.

Commercially Confidential Information

Commercially Confidential Information

Commercially Confidential Information

4.5.6 Injection site reaction

Commercially Confidential Information

4.5.7 Hypoglycemia

The risk of hypoglycemia in participants with T2DM in this study is low. Weight loss itself is not associated with hypoglycemia. Medications that increase the risk of hypoglycemia with weight loss are those that induce insulin secretion such as sulfonylureas and insulin. These are excluded in this study.

Commercially Confidential Information

Commercially Confidential Information

4.5.9 Blood sample volume

The total volume of blood collected over a period of approximately 27 weeks is smaller than the volume of a typical blood donation. This sampling will be performed in each participant of the study. Additional samples may be required for safety monitoring.

Timings of blood sample collection are outlined in the assessment schedule [Table 8-1](#).

A summary blood log is provided in the laboratory manual. Instructions for sample collection, processing, storage and shipment information are also available in the laboratory manual.

See the [Section 8.5.3.1](#) on the potential use of residual samples.

4.5.10 Potential risk associated with the COVID-19 pandemic

Novartis is committed to supporting the safety and well-being of our study participants, investigators, and site staff. All local regulations and site requirements are being applied in the countries that are affected by the COVID-19 pandemic, including COVID-19 testing of participants if applicable. The Novartis clinical trial team will review the situation in each participating country and work with investigators to continue to ensure the safety of participants during the conduct of the trial. A benefit/risk assessment has been made and has been determined to be positive for the participants to be enrolled. As the COVID-19 situation evolves, investigators must use their best judgement to minimize risk to participants during the conduct of the study. Study specific details of vaccination of COVID-19 is provided in [Section 8.1.1.3](#) of the protocol.

MBL949 is not an immunosuppressive agent, and is not expected to compromise participants' immune systems.

4.5.11 New diagnosis of T2DM

Per standard of care, typically individuals with a new diagnosis of T2DM receive counseling on diet and exercise through their health care provide and dietitian. Evaluation of diet and exercise usually proceeds for 3-4 months after which initiation of an anti-diabetes drug is typically prescribed if diet and exercise therapy are ineffective. Thus enrollment in the study would not materially change or delay T2DM management.

Commercially Confidential Information

Commercially Confidential Information

4.7 Rationale for Public Health Emergency mitigation

In Commercially Confidential Information the event of a Public Health emergency as declared by Local or Regional authorities i.e., pandemic, epidemic or natural disaster, additional mitigation procedures to ensure participant safety and trial integrity may be implemented. If allowable by a local Health Authority and depending on operational capabilities, phone calls, virtual contacts (e.g. tele consult) or additional visits by OHPs to the participant's home, can replace onsite study visits (in addition to the already planned off-site visits), for the duration of the disruption until it is safe for the participant to visit the site again.

Notification of the Public health emergency should be discussed with Novartis prior to implementation of mitigation procedures and permitted/approved by Local or Regional Health Authorities and Ethics Committees as appropriate.

5 Study Population

The study population will include obese (BMI ≥ 32 kg/m²) men and women between 18 and 60 years of age with or without T2DM. To account for 15% drop out rate, approximately 106 participants are planned to be randomized to achieve 90 total completers. The Investigator must ensure that all participants being considered for the study meet the following eligibility criteria. No additional criteria should be applied by the Investigator, in order that the study population will be representative of all eligible participants. Participant selection is to be established by checking through all eligibility criteria at both screening, baseline, and prior to randomization as applicable. A relevant record (e.g., checklist) of the eligibility criteria must be stored with the source documentation at the site. Deviation from any entry criterion excludes a participant from enrollment into the study.

5.1 Inclusion criteria

Participants eligible for inclusion in this study must meet **all** of the following criteria:

ALL PARTICIPANTS

1. Written informed consent must be obtained before any assessment is performed.
2. Able to communicate well with the investigator, to understand and comply with the requirements of the study.
3. At screening, men and women must be between 18 and 60 years of age inclusive
4. At screening, participants must have a body mass index: $\geq 32 \text{ kg/m}^2$, weight $\geq 77 \text{ kg}$, stable body weight i.e., less than 1.5 kg self-reported change within 90 days and/or 3 kg self-reported change within 6 months prior to screening [BMI = Weight (kg) / [Height (m)]²

PARTICIPANTS WITH T2DM

5. Diagnosed T2DM as documented by medical history and confirmed by Investigator and with diagnosed duration < 10 yrs, HbA1c $\leq 9\%$, and fasting C-peptide $\geq 0.2 \text{ ng/ml}$
6. If treated for T2DM, treatment must be limited to diet and exercise and treatment with **one** of the following anti-diabetic agents is permitted (stable for 90 days prior to randomization):
 - Metformin
 - SGLT2i inhibitors (if prescribed as the first line, i.e. single agent)
 - DPP4 inhibitors
 - Acarbose

5.2 Exclusion criteria

Participants meeting any of the following criteria are not eligible for inclusion in this study.

ALL PARTICIPANTS

1. At screening, vital signs (blood pressure and pulse rate) will be assessed in the sitting position (see [Table 8-2](#) for detailed description on vital signs methodology). The sitting vital signs defined below are exclusionary:
 - systolic blood pressure less than 95 mm Hg or greater than 155 mm Hg
 - diastolic blood pressure less than 60 mm Hg or greater than 95 mm Hg
 - pulse rate less than 56 or greater than 110 bpm

Commercially Confidential Information

2. History of bariatric surgery, Roux-en-Y Gastric Bypass, Sleeve Gastrectomy, gastric banding, and any other intra abdominal procedures designed for weight loss at screening

Commercially Confidential Information

3. Commercially Confidential Information

4. History of myocardial infarction within 2 years of screening
5. Commercially Confidential Information

- 6.
- 7.

- 8.

9. Diet attempts using herbal supplements or over-the-counter medications within 90 days before screening
10. Participation in an organized weight reduction program (e.g. WeightWatchers, NutriSystem) or any investigational weight loss trial within 6 months before screening
11. Commercially Confidential Information

- 12.

- 13.
- 14.
- 15.

- 16.
- 17.

- 18.

- 19.

20. Commercially Confidential Information

21.

22.

23.

24.

25.

26.

27.

Commercially Confidential Information

28.

PARTICIPANTS WITH T2DM

29. Commercially Confidential Information

30.

31.

6 Treatment

6.1 Study treatment

Details on the requirements for storage and management of study treatment, and instructions to be followed for participant numbering, prescribing/dispensing, and taking study treatment are outlined in the Pharmacy Manual.

6.1.1 Investigational and control drugs

Table 6-1 Investigational and control drug

Investigational/ Control Drug (Name and Strength)	Pharmaceutical Dosage Form	Route of Administration	Supply Type	Sponsor (global or local)
MBL949 10 mg/mL	Solution for injection	Subcutaneous Use	Open label; bulk supplies	Sponsor (global)
Placebo 0 mg/mL	Solution for injection	Subcutaneous Use	Open label; bulk supplies	Sponsor (global)

The investigational drug, MBL949 10 mg/mL and placebo, will be prepared by Novartis and supplied to the Investigator as an open labeled medication to be dispensed by the unblinded pharmacist or designated staff at the investigator site according to the randomization schedule. Study medication will be administered by an unblinded staff at the site.

MBL949 drug product is formulated for subcutaneous injection as 10 mg/mL liquid in vial. Details of the dose administration can be found in the Pharmacy Manual.

Each vial of MBL949 contains 10 mg of drug product formulated as a solution for injection. In addition to the active substance, each vial contains the following excipients: CCI

A 20% overfill is provided to allow the withdrawal of the designated amount of 10 mg/mL MBL949 upon administration.

MBL949 10 mg solution for injection is packaged in glass vials with coated rubber stoppers sealed with aluminum caps with plastic flip-off disks, which are in common use for packaging of parenteral products.

6.1.2 Additional study treatments

No other treatment beyond investigational drug and control drug are included in this trial.

6.1.3 Treatment arms/group

Participants will be assigned to one of five arms in this study; MBL949 dosing arms 1-5 and placebo arm. MBL949 Arm 1, MBL949 arm 2 and placebo to be enrolled in a 1:1:1 ratio in each randomization stratum. MBL949 arm 3 and MBL949 arm 4 and placebo will be enrolled in a 1:1:1 ratio in each randomization stratum. If triggered, MBL949 dosing arm 5 will be randomized in a 2:1 ratio of MBL949 or placebo. Refer to [Section 3](#) for study design in [Figure 3-1](#) and enrollment flow [Figure 3-2](#).

Study treatments are defined as:

- Once every other week SC injection of MBL949 mg, for dosing details refer to [Section 4.2](#)
- Once every other week SC injection of Placebo 0 mg

Commercially Confidential Information

6.2 Other treatment(s)

6.2.1 Concomitant therapy

All medications, procedures, and significant non-drug therapies (including physical therapy and blood transfusions) administered after the participant was enrolled into the study must be recorded on the appropriate Case Report Forms.

Each concomitant drug must be individually assessed against all exclusion criteria/prohibited medication. If in doubt, the investigator should contact the Novartis medical monitor before randomizing a participant or allowing a new medication to be started. If the participant is

already enrolled, contact Novartis to determine if the participant should continue participation in the study.

Medications allowed in the study as chronic therapy:

- Oral anti-diabetic therapy (limited to metformin and/or DPP4 inhibitor or acarbose), with stable treatment for 90 days prior to randomization, for diabetes management during the trial.
- Treatment with SGLT2i (permitted if first line agent)

Commercially Confidential Information

6.2.2 Prohibited medication

Use of the treatments displayed in the below table are not allowed per the prohibition period below.

Table 6-2 Prohibited medication

Medication	Prohibition period	Action taken
Over the counter anti-obesity medications, nutritional supplements, dietary interventions particularly chromium picolinate and sodium vanadate (other than described in protocol) or over the counter products of weight loss	Within 90 days prior to randomization and through duration of study	Discontinue study treatment
Prescription anti obesity agents and GLP1 receptor agonists such as (e.g., semaglutide, exenatide, liraglutide, lixisenitide, albiglutide, dulaglutide) Refer to Section 5.2 Sulfonylureas or thiazolidinediones Insulin	Within 6 months prior to randomization and through duration of study	Discontinue study treatment

6.2.3 Restriction for study participants

For the duration of the study, participants should be informed and reminded of the restrictions outlined in this section.

Commercially Confidential Information

6.3 Participant numbering, treatment assignment, randomization

6.3.1 Participant numbering

Each participant is identified in the study by a Participant Number (Participant No.), that is assigned when the participant is enrolled for screening and is retained for the participant throughout his/her participation in the trial. A new Participant No. will be assigned at every subsequent enrollment if the participant is re-screened. The Participant No. consists of the Center Number (Center No.) (as assigned by Novartis to the investigative site) with a sequential participant number suffixed to it, so that each participant's participation is numbered uniquely across the entire database. Upon signing the informed consent form, the participant is assigned to the next sequential Participant No. available.

A new ICF will need to be signed if the investigator chooses to re-screen the participant after a participant has screen failed, and the participant will be assigned a new Participant No.

6.3.2 Treatment assignment, randomization

Randomization for this study will be managed by Novartis Interactive Response Technology (IRT). The randomization numbers will be generated using the following procedure to ensure

that treatment assignment is unbiased and concealed from participants and investigator staff. A participant randomization list will be produced by the IRT provider, or by a delegate under Novartis supervision, using a validated system that automates the random assignment of participant numbers to randomization numbers. These randomization numbers are linked to the different treatment arms.

Commercially Confidential Information

The randomization scheme for participants will be reviewed and approved by a member of the Randomization Office.

6.4 Treatment blinding

This is a participant-and investigator-blinded, sponsor open-label study. Participants and investigators will remain blinded to study treatment throughout the study, except where indicated below.

The identity of the treatments will be concealed by the use of study drugs that are all identical in packaging, labeling, schedule of administration, appearance, and odor.

Site staff

With the exception of any unblinded site staff listed below, all site staff (including study investigator, study nurse, CCI) will be blinded to study treatment throughout the study.

- Designated unblinded site staff, CCI for dose administration: required due to the range of different dose levels and to maintain the investigator and site staff blinding.
- Unblinded pharmacist who is independent of the study team will be required in order to manage drug product supplied in bulk and prepare doses.

This unblinded pharmacist will receive a randomization assignments via IRT. Appropriate measures must be taken by the unblinded pharmacist to ensure that the treatment assignments are concealed from the rest of the site staff, with the exception of the designated unblinded site staff who will administer the dose.

Unblinding a single participant at site for safety reasons (necessary for participant management) will occur via the IRT system.

Sponsor staff

The following unblinded sponsor roles are required for this study:

- Unblinded field monitor(s)
- Unblinded clinical staff managing drug re-supply to site
- Commercially Confidential Information

The unblinded field monitors are required to review drug accountability and allocation at site. The unblinded monitors are not provided with a randomization list directly but will be unblinded through review of source documentation compiled by the unblinded pharmacist, which details treatment allocation to individual participants. The unblinded monitors will also be able to review the treatment allocation cards/randomization list provided to the unblinded pharmacist. The names of the unblinded monitor(s) are detailed in the monitoring plan.

Sponsor clinical staff are required to assist in the management and re-supply of investigational drug product. These individuals are not provided with randomization lists directly, but may be unblinded through communication of drug re-supply needs via the unblinded site pharmacists.

Commercially Confidential Information

The study statistician will be able to access the randomization list at any time throughout the study and is allowed to share unblinded information with the rest of the clinical team including an unblinded study lead and Trial Medical Expert as appropriate for internal decision purposes, as outlined in [Table 6-3](#).

Commercially Confidential Information

All unblinded personnel will otherwise keep randomization lists and data or information that could unblind other study team members confidential and secure except as described above.

Following final database lock all roles may be considered unblinded.

Table 6-3 Blinding levels

Role	Time or Event			
	Randomization list generated	Treatment allocation & dosing	Safety event (single subject unblinded)	CCI dose escalation
Subjects/Patients	B	B	UI	B
Site staff	B	B	UI	B
Unblinded site staff (see text for details)	B	UI	UI	UI
Drug Supply and Randomization Office	UI	UI	UI	UI
Unblinded sponsor staff (see text for details)	B	UI	UI	UI
Statistician/statistical programmer/data analysts	B	UI	UI	UI
All other sponsor staff not identified above	B	UI	UI	UI

B Remains blinded

UI Allowed to be unblinded on individual patient level

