8.1 Screening

Screening

It is permissible to re-screen a participant if s/he fails the initial screening and reason for screen fail is reasonably expected to have resolved; however, each case must be discussed and agreed with the Sponsor on a case-by-case basis.

In the case where a safety laboratory assessment at screening is outside of the range specified in the exclusion criteria, the assessment may be repeated once prior to randomization. If the repeat value remains outside of the specified ranges, the participant must be excluded from the study.

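### Protocol 6.4 opens the randomization list to the study statistician at any time, Table 6-3 does not, and the visible text does not confine access or sharing to participants already randomized

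*Protocol*

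**What the plan says.** Protocol 6.4 (Treatment blinding) declares the study blinded for participants and investigators and open-label for the sponsor. On the list itself it says: "The study statistician will be able to access the randomization list at any time throughout the study and is allowed to share unblinded information". Among the recipients it names the study lead and the Trial Medical Expert, and it qualifies the sharing with "as appropriate for internal decision purposes, as outlined in" Table 6-3. A later sentence requires unblinded personnel to keep lists and unblinding information secure, but exempts what has just been permitted.

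Table 6-3 (Blinding levels) has a row headed "Statistician/statistical programmer/data analysts" and a separate row for all remaining sponsor staff. It defines unblinding as being at the level of the individual patient.

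The sponsor also has a part in some entries:
- Protocol 8.1 allows re-screening, but "each case must be discussed and agreed with the Sponsor on a case-by-case basis".
- Protocol 6.2.1 says of concomitant drugs: "If in doubt, the investigator should contact the Novartis medical monitor before randomizing a participant or allowing a new medication to be started".
- Protocol 8.4.2 requires clinically significant baseline ECG findings to be discussed with the sponsor before study treatment is given.

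On the site pharmacist, 6.4 says that assignments arrive via IRT. It also says that unblinded monitors can "review the treatment allocation cards/randomization list provided to the unblinded pharmacist".

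**The concern.** A randomization list differs in kind from a record of assignments already made, because while enrollment is open it also holds entries not yet used. A sponsor-open-label design needs the treatment of people already randomized, for safety review and internal decisions. It does not need the upcoming entries. If upcoming entries can be seen, and the information can travel to colleagues, allocation concealment depends on who happens to be consulted about a candidate's entry and not on a rule in the protocol. At stake is the protection that randomization gives to both primary comparisons, weight change at week 16 and adverse events.

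**Working it through.** No figure in the plan is in question, so the check sets the texts side by side.

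**1. The sentence against the table.** The relevant rows of Table 6-3 are (B = blinded, UI = may be unblinded for individual patients):

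| Role | List generated | Allocation and dosing |
|---|---|---|
| Statistician, programmer, analysts | B | UI |
| All other sponsor staff | B | UI |
| Unblinded sponsor staff | B | UI |
| Unblinded site staff | B | UI |
| Drug Supply and Randomization Office | UI | UI |

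Only Drug Supply and the Randomization Office are unblinded at the list stage. The text gives the statistician the list with no restriction on timing. Both statements are fully visible, and they disagree on when and at what level the statistician is unblinded.

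**2. What the list holds.** Under 6.3.2 the IRT provider or a delegate produces a list whose randomization numbers are linked to arms. Table 6-3 treats its generation as a separate event from allocation. During enrollment such a list contains unused entries. Section 6.4 itself treats lists as more sensitive than single assignments, since monitors and re-supply staff are not handed lists directly. No such limit is stated for the statistician.

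**3. Visible safeguards.** Section 6.3.2 promises concealment from participants and the investigator's staff, and does not mention the sponsor. The confidentiality sentence in 6.4 exempts the sharing described before it. No visible sentence withholds unused entries from the statistician or bars passing them on. Redacted blocks sit in 6.3.2, in the 6.4 list of unblinded sponsor roles, and directly after the sentence on the statistician.

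**4. The sponsor's part in entry.** Section 5 makes the investigator responsible for eligibility against fixed criteria. The sponsor comes in only for re-screening, concomitant-drug doubts and baseline ECG findings. Nothing visible says that the study lead or the Trial Medical Expert handles these contacts, and nothing visible says that they do not.

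**5. The pharmacist.** Receiving assignments through IRT and holding a randomization list are two different arrangements. The second also fits poorly with the B for unblinded site staff at list generation.

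**6. What a list would add.** Sections 3 and 6.1.3 give 1:1:1 allocation in the first two stages and 2:1 for arm 5. Ignoring block structure, which is not visible:
- exact arm without the list, 1:1:1: 1/3;
- active versus placebo without the list, always guessing active: 2/3 under 1:1:1 and 2/3 under 2:1;
- with the unused entries and the next position in the stratum: 1.

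**7. Why this yields no bias in kilograms.** The shift in an arm mean would be (share of entries steered) × (difference in expected weight change). The documents give neither input, nor any count of re-screens or pre-randomization queries. The 2 kg in 12.8.1 cannot serve as a yardstick: it is an assumed change of -2 kg within arm 4, not a difference from placebo, and no placebo assumption is visible.

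**The case against.** The strongest reply is that the sentence carries its own limit. What may be shared is unblinded information, not the list by name; the sharing is for internal decisions and within Table 6-3; and the table works patient by patient from allocation onward. Read that way, only allocated participants are covered. This is a fair reading of the sharing clause, and probably the intended one. It does not reach the access clause, which has no such limit, and it leaves the conflict with the table in place.

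A reader might infer that sponsor staff who decide on entry know the next assignment. The documents do not support that. The investigator decides eligibility, and the sponsor's input is confined to particular cases. No passage identifies those who answer such questions with those who may receive unblinded information. The only study-team role visibly given the list is the statistician, who has no stated part in eligibility. That recipients would learn unused entries is left open by silence; it is not stated.

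Timing also weakens the re-screening route. Screening runs from Day -35 to Day -15 and randomization is on Day 1, so at least about two weeks of multi-center enrollment follow the sponsor's agreement. Even someone holding the list could not then be sure which entry the candidate would receive. The point has less force for questions raised shortly before randomization.

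Two further replies stand. The sponsor's open-label status is declared and is not itself a flaw. The redacted blocks lie where an access limit might be written, so one may exist. The pharmacist, who is independent of the study team and has no entry role, adds an inconsistency in wording but no route to selection.

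**Conclusion.** The point holds in a narrow form. The text of 6.4 and Table 6-3 disagree on the statistician's access to the randomization list, and the visible text does not confine access or sharing to participants already randomized, although the sponsor has a say in some individual entries.

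This is a weakness in how concealment is specified. It does not show that concealment fails or that selection would occur, and no magnitude can be attached to it. The conclusion assumes that the list is prepared ahead of allocation, as 6.3.2 and Table 6-3 indicate, and that the redacted text does not already impose the limit. If it does, the conflict between the visible sentence and the table remains and still needs correcting. The change is worth making because it is nearly free and gives up nothing that the open-label sponsor role requires.

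**What to change.** Reword 6.4 to follow Table 6-3, for example:

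*The study statistician may access, and may share for internal decisions, the assignments of participants already randomized. Unused entries of the randomization list remain with the Randomization Office and IRT, and with Drug Supply as shown in Table 6-3, until enrollment closes.*

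Add a sentence that sponsor staff consulted on re-screening, eligibility or concomitant-drug questions before randomization have no access to unused entries. Reconcile the mention of a list held by the unblinded pharmacist with the statement that assignments reach the pharmacist through IRT. If a redacted passage already sets these limits, refer to it from the sentence on the statistician.

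The cost is protocol wording and an IRT access setting. Codes of treated participants remain available for safety review and internal decisions, and no analysis changes.
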